### **9.1.3. Study Period**

No study drug will be administered.

The medical follow-up of the subjects will be performed according to the local standard of care during the assessment period.

At each study site visit (3, 6, 12, 18, and 24 months after entry visit) as noted in the [Time and Events Schedule](#) and during a monthly telephone call (calendar month  $\pm 7$  days), a clinical questionnaire (see [Attachment 2](#)) will be completed by a study site responsible person, by interviewing the subject’s parent/caregiver, to collect the following information:

- Wheezing.  
The parent/caregiver will be provided with a wheezing parent/caregiver card to be completed daily (see [Attachment 3](#)) which will aid the site responsible person in completing the questionnaire.
- Diagnosis of asthma, eczema, and allergic rhinitis. All medical information needed to confirm the diagnosis of asthma, eczema, and allergic rhinitis needs to be collected by the study site personnel.
- Impact of the subject’s health status on normal daily activities for subjects, parents/caregivers, and other family members.

Medical resource utilization data will be collected throughout the study.

Parents/caregivers will also be provided with a medication parent/caregiver card to record medication use on a daily basis (see [Attachment 4](#)).

Parents/caregivers will be required to return the completed wheezing and medication parent/caregiver cards to the study sites every 3 months (eg, in person or by mail/email/fax when no study site visit is scheduled).

## **9.2. Clinical Evaluations**

The study includes the following clinical evaluations:

- Collection of information on the clinical diagnosis of asthma to determine the incidence of asthma.
- Collection of presence of wheezing on a daily basis to determine the frequency of wheezing and wheezing episodes.

- Collection of medical history and family history to identify risk factors for wheezing/asthma at baseline.
- Collection of data to determine the frequency and type of respiratory infections.
- Collection of data on medications used for the treatment of respiratory infections and illnesses (eg, bronchodilators).
- Collection of data from lung function tests and allergy tests (immunoglobulin E and skin test), if available, as supporting documentation of the diagnosis of asthma, wheezing, and atopy.

### **9.3. Medical Resource Utilization and Health Economics**

Medical resource usage (including medical visits, emergency room visits, and hospitalizations, all for respiratory conditions) and the impact of the subject's health status on normal daily activities for subjects, parents/caregivers, and other family members will be collected throughout the course of the study.

### **9.4. Safety Evaluations**

Any SAEs or reportable AEs occurring during the study must be recorded on the AE section of the eCRF.

The following AEs will be considered reportable (within the context of this study):

- Respiratory illness AEs, including subsequent RSV infections.
- AEs considered at least possibly related to lumicitabine or placebo.
- SAEs (defined in Section 12.1.1).

The study will include the following evaluations of safety and tolerability according to the time points provided in the [Time and Events Schedule](#).

### **Adverse Events**

Reportable AEs will be reported by the subject's parent/caregiver (or the subject's legally acceptable representative) for the duration of the study.

Any reportable AEs persisting at the end of the study will be followed by the investigator until resolution or until a clinically stable endpoint is reached.

### **9.5. Sample Collection and Handling**

No safety or PK blood sampling will be performed.

## **10. SUBJECT COMPLETION/WITHDRAWAL FROM THE STUDY**

### **10.1. Completion**

A subject will be considered to have completed the study if he or she has completed assessments at Month 24 of the assessment period (or until the last assessment, if the study is extended).

## 10.2. Withdrawal From the Study

A subject will be automatically withdrawn from the study for any of the following reasons:

- Lost to follow-up.
- Withdrawal of consent.
- Death.

If a subject is lost to follow-up, every reasonable effort must be made by the study site personnel to contact the parent/caregiver and determine the reason for withdrawal. The measures taken to follow up must be documented.

When a subject is withdrawn by his/her parent(s)/caregiver(s) before completing the study, the reason for withdrawal is to be documented in the eCRF and in the source document.

## 11. STATISTICAL METHODS

Statistical analyses will be performed by a qualified vendor under the supervision/responsibility of the sponsor.

### 11.1. Subject Information

All subjects whose parent/caregiver provides informed consent will be included in the analysis. Demographics and other baseline characteristics will be summarized descriptively.

### 11.2. Sample Size Determination

No formal power calculation has been performed, as this is an LTFU study in which infants and children from the previous Phase 2 study of lumicitabine (Study 64041575RSV2004) may be enrolled.

The planned number of subjects enrolled in Study 64041575RSV2004 is up to 120 subjects on lumicitabine and up to 60 subjects on placebo. It is expected that approximately 35% of those subjects will participate in this LTFU study.

### 11.3. Clinical Analyses

The final analysis will be done when all the subjects have completed the last planned assessment of this LTFU study or discontinued earlier.

#### 11.3.1. Primary Analysis

The primary endpoints in this study are the clinical diagnosis of asthma and the percentage of wheezing days in a subject within the first 2 years after the RSV infection, as reported by the parent/caregiver.

No statistical testing will be done.

Estimates of the incidence of asthma will be presented together with the 95% (2-sided) confidence interval (CI) by previous treatment group. The previous treatment group is defined as

the actual treatment of the Study 64041575RSV2004. As a sensitivity analysis, the incidence of asthma will be presented for the subgroup of subjects for whom at least 12 months of follow-up data are available.

The percentage of days with wheezing within the first 2 years after the RSV infection will be calculated per subject. Descriptive statistics, including 95% CIs, will be presented by previous treatment group.

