### **STATISTICAL METHODS**

No formal power calculation has been performed, as this is an LTFU study in which infants and children from the previous Phase 2 study of lumicitabine (Study 64041575RSV2004) may be enrolled. The planned number of subjects enrolled in Study 64041575RSV2004 is up to 120 subjects on lumicitabine

and up to 60 subjects on placebo. It is expected that approximately 35% of those subjects will participate in this LTFU study.

The final analysis will be done when all the subjects have completed the last planned assessment of the follow-up period or discontinued earlier.

The primary endpoints in this study are the clinical diagnosis of asthma and the percentage of wheezing days in a subject within the first 2 years after the RSV infection, as reported by the parent/caregiver.

No statistical testing will be done.

Estimates of the incidence of asthma will be presented together with the 95% (2-sided) confidence interval by previous treatment group. The previous treatment group is defined as the actual treatment (lumicitabine or placebo) of Study 64041575RSV2004. As a sensitivity analysis, the incidence of asthma will be presented for the subgroup of subjects for whom at least 12 months of follow-up data are available.

The percentage of days with wheezing within the first 2 years after the RSV infection will be calculated per subject. Descriptive statistics, including 95% confidence intervals, will be presented by previous treatment group.

For the secondary endpoint, descriptive statistics and frequency tabulations will be used to present the percentage of wheezing days per month, the mean number of wheezing episodes, and the number and type of respiratory infections by previous treatment group.

Long-term safety of lumicitabine, medical resource utilization, and impact of the subject's health status on normal daily activities for subjects, parents/caregivers, and other family members will be evaluated using frequency tabulations and listings by previous treatment group.

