## 2.2. Hypothesis

No formal hypothesis testing will be performed. The hypothesis to be explored is that treatment of RSV-infected infants and children with lumicitabine will decrease the incidence of subsequent asthma and/or wheezing compared with infants and children treated with placebo.

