### **11.3.2. Secondary Analysis**

Descriptive statistics and frequency tabulations will be used to present the percentage of wheezing days per month, the mean number of wheezing episodes, and the number and type of respiratory infections by previous treatment group.

As a sensitivity analysis, 2 different imputations for missing data will be performed:

- Missing values will be replaced with the mean of the previous and subsequent month of the subject. When values at the end of the second follow-up year are missing, these missing values will be replaced by the mean of the previous month and the same month of the previous year. Thus, missing values will be replaced by values that are completely dependent on observations of the same subject.
- Missing values will be imputed by the mean of non-missing values of other subjects during the same month of the same follow-up year of the same treatment group. Thus, with this approach, missing values will be replaced by values that are independent of observations from the same subject.

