### **11.4. Medical Resource Utilization and Health Economics Analyses**

Medical resource utilization will be evaluated using frequency tabulations and listings by previous treatment group.

The impact of the subject's health status on normal daily activities for subjects, parents/caregivers, and other family members will be evaluated using frequency tabulations and listings by previous treatment group.

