### **11.5. Safety Analyses**

#### **Adverse Events**

The verbatim terms used in the eCRF by investigators to identify the reportable AEs and SAEs will be coded using the Medical Dictionary for Regulatory Activities. For each reportable AE and SAE, the percentage of subjects who experience at least 1 occurrence of the given event will be summarized by previous treatment group. In addition, comparisons between previous treatment groups will be provided if appropriate.

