2.3. Analysis Sets

2.3.1. All Enrolled Analysis Set

The All Enrolled analysis set includes all subjects who were enrolled in this LTFU study. The All Enrolled set will be analyzed as treated.

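### Efficacy endpoints are grouped by treatment received, with no presentation by randomised arm, so a child given the other arm's product in the parent study would count in that other arm

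*Protocol*

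**What the plan says.** The protocol synopsis (Statistical Methods) sets the rule: "The previous treatment group is defined as the actual treatment (lumicitabine or placebo) of Study 64041575RSV2004". Protocol 11.3.1 repeats it for the primary asthma analysis, where the group is "the actual treatment of the Study 64041575RSV2004". SAP 2.3.1 has one analysis set and says: "The All Enrolled set will be analyzed as treated".

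The grouping then runs through the plan:

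- Wheezing days, co-primary (Protocol 11.3.1): "Descriptive statistics, including 95% CIs, will be presented by previous treatment group".
- Secondary endpoints (Protocol 11.3.2): wheezing days per month, wheezing episodes and "the number and type of respiratory infections by previous treatment group".
- Resource use (Protocol 11.4): "Medical resource utilization will be evaluated using frequency tabulations and listings by previous treatment group". The impact on daily activities is handled the same way.
- Safety (Protocol 11.5): the percentage of subjects with "at least 1 occurrence of the given event will be summarized by previous treatment group".

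Neither document plans a presentation by randomised arm, even as a sensitivity analysis. Neither specifies a listing that sets randomised treatment beside actual treatment.

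**The concern.** SAP section 5 is headed Efficacy, and SAP 5.1.2 states an estimand: the lumicitabine-minus-placebo difference in the proportion diagnosed with asthma, evaluated descriptively. The hypothesis in Protocol 2.2 is that lumicitabine "will decrease the incidence of subsequent asthma and/or wheezing compared with infants and children treated with placebo". The children were randomised in a double-blind, placebo-controlled parent study.

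For a contrast of that kind the usual grouping is the arm to which the child was allocated. Grouping by treatment received is the usual choice for safety tables. This plan applies the safety convention to everything and gives no reason.

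At stake is the placement of any child who received the other arm's product. That child leaves one arm's numerator and denominator and enters the other's. In arms this small, one such move can dominate the difference, and no specified output would show that it had happened.

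**Working it through.** The plan gives no power, test or effect size to reproduce. The check is therefore a reading of the grouping rule, followed by an illustration of what one reclassified child would do.

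**Which errors move a child.** The synopsis gives the grouping two levels, lumicitabine or placebo. A missed dose, a wrong amount or a mix-up between lumicitabine regimens leaves the level unchanged. Only receipt of the other arm's product can change it. The documents do not say how a child exposed to both products would be classed.

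**Inputs from the documents.**

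- Parent study: up to 120 on lumicitabine and up to 60 on placebo, with about 35% expected to join (Protocol 11.2). Expected size: 0.35 × 120 = 42 and 0.35 × 60 = 21.
- Actual enrolment: 7 children (SAP 2.4).
- Intervals: 95% two-sided Wilson (SAP 5.1.3).

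**Inputs assumed.** The split of the 7 children, the number of asthma cases, and the existence of one wrong-product child. The documents give none of these.

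**Formula.** Difference = (asthma cases / n on lumicitabine) − (asthma cases / n on placebo), in percentage points.

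**Seven children.** Assume one asthma case, in a child randomised to placebo who received lumicitabine.

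| Randomised split (lumicitabine:placebo) | By randomised arm | As treated |
|---|---|---|
| 3:4 | 0/3 − 1/4 = −25.0 | 1/4 − 0/3 = +25.0 |
| 4:3 | 0/4 − 1/3 = −33.3 | 1/5 − 0/2 = +20.0 |
| 5:2 | 0/5 − 1/2 = −50.0 | 1/6 − 0/1 = +16.7 |

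At 6:1 the as-treated placebo group would be empty and no difference could be formed. If the moved child is not the case, the sign holds but the size changes: at 4:3, −33.3 becomes 0/5 − 1/2 = −50.0.

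**Width of the intervals.** Wilson limits are [p + z²/2n ± z√(p(1−p)/n + z²/4n²)] / (1 + z²/n), with z = 1.96. For 1/3 they are 6.1% to 79.2%. For 1/5 they are 3.6% to 62.4%.

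**Expected size of 42:21.** Two sets of assumed counts:

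- Equal rates, 8/42 and 4/21 (19.0% each), difference 0. If one asthma case randomised to lumicitabine had received placebo, the as-treated figures are 7/41 = 17.1% and 5/22 = 22.7%, a difference of −5.7 points.
- 3/42 and 4/21, difference 7.1% − 19.0% = −11.9 points. One case moved from placebo to lumicitabine gives 4/43 − 3/20 = −5.7. One case moved the other way gives 2/41 − 5/22 = −17.8.

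**No wrong-product child.** The two groupings are identical and the change is 0.

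**The case against.** The strongest reply is that the rule may have no effect at all. Nothing in either document reports or suggests that a child received the wrong product. The rule is prespecified and consistent across protocol and SAP. The objectives and hypothesis are worded in terms of children treated with one product or the other, and there is no formal test, so no error rate is at stake. With 7 children the intervals are too wide to support a conclusion under either grouping. All of this stands, and it is why the point is minor. It does not supply a reason for using the safety convention in the efficacy tables, or for leaving a discordant child invisible.

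A second reply also stands. Participation is optional for sites, about 35% of subjects were expected to join, and entry requires completion of the planned drug course and of the last parent-study visit. These children are already a selected group of completers, so regrouping by randomised arm cannot recover the parent study's randomised comparison.

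Two stronger readings are tempting. A reader might infer that any dosing error in the parent study moves a child between arms. The two-level grouping rules that out. A reader might also infer that every endpoint is affected. That is slightly too broad, since no treatment-group analysis is described for the wheezing/asthma phenotype endpoint.

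**Conclusion.** The plan groups asthma, wheezing, respiratory infections, resource use and burden by treatment received, offers no view by randomised arm, and would not reveal a discordant child. For the difference in SAP 5.1.2, grouping by the parent allocation is the better default.

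The size is conditional. One misallocated asthma case among 7 children could reverse the sign of the descriptive difference under each of the 3:4, 4:3 and 5:2 splits. That rests on an assumed split, an assumed single case and an assumed wrong-product child. If there is no such child, nothing changes. The documents do not support a claim that the results are biased, only that the plan leaves an avoidable exposure open and unreported. Severity is low.

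**What to change.** In the SAP, and in the protocol synopsis and 11.3.1 if the protocol is amended for another reason:

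- Present asthma, wheezing, respiratory infections, resource use and burden by the arm randomised in Study 64041575RSV2004.
- Keep actual treatment for reportable adverse events and serious adverse events (Protocol 11.5, SAP section 6), and say how a child exposed to both products would be classed there.
- List any child whose randomised and actual treatment differ, or state that the two coincide for all 7.
- Label each table with its grouping. SAP Table 2 derives respiratory infections from adverse event terms, so the same events can appear under both rules.
- Say in the report that grouping by randomised arm removes one departure from the parent allocation and leaves the selection into follow-up as it is.

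The cost is a few lines of SAP text and one more variable from the parent-study database, from which the SAP already takes baseline data. With no test planned, there is no loss of power. SAP section 3 says the project was stopped, so a protocol amendment for this alone is not worthwhile. If the two assignments coincide for all 7 children, one sentence to that effect settles the point.

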### **11.3.2. Secondary Analysis**

Descriptive statistics and frequency tabulations will be used to present the percentage of wheezing days per month, the mean number of wheezing episodes, and the number and type of respiratory infections by previous treatment group.

As a sensitivity analysis, 2 different imputations for missing data will be performed:

- Missing values will be replaced with the mean of the previous and subsequent month of the subject. When values at the end of the second follow-up year are missing, these missing values will be replaced by the mean of the previous month and the same month of the previous year. Thus, missing values will be replaced by values that are completely dependent on observations of the same subject.
- Missing values will be imputed by the mean of non-missing values of other subjects during the same month of the same follow-up year of the same treatment group. Thus, with this approach, missing values will be replaced by values that are independent of observations from the same subject.

### **11.4. Medical Resource Utilization and Health Economics Analyses**

Medical resource utilization will be evaluated using frequency tabulations and listings by previous treatment group.

The impact of the subject's health status on normal daily activities for subjects, parents/caregivers, and other family members will be evaluated using frequency tabulations and listings by previous treatment group.

### **11.5. Safety Analyses**

#### **Adverse Events**

The verbatim terms used in the eCRF by investigators to identify the reportable AEs and SAEs will be coded using the Medical Dictionary for Regulatory Activities. For each reportable AE and SAE, the percentage of subjects who experience at least 1 occurrence of the given event will be summarized by previous treatment group. In addition, comparisons between previous treatment groups will be provided if appropriate.

### **11.6. Interim Analysis**

An unblinded interim analysis will be performed when all subjects from the first season in Study 64041575RSV2004 who are enrolled in this LTFU study complete the 18 month

follow-up assessment of this LTFU study. This interim analysis will serve to evaluate the need for an extension of the follow-up period. The interim analysis will use all available data; the results will be presented by previous treatment group, using descriptive statistics.

Based on this interim review, the study may be extended up to an additional 3 years (ie, total duration up to 5 years after randomization into Study 64041575RSV2004). In the event that the study is extended, the parents/caregivers of subjects will be required to provide additional informed consent.

Additional interim analyses may be performed for regulatory purposes.

## **12. ADVERSE EVENT REPORTING**

Timely, accurate, and complete reporting and analysis of safety information from clinical studies are crucial for the protection of subjects, investigators, and the sponsor, and are mandated by regulatory agencies worldwide. The sponsor has established standard operating procedures in conformity with regulatory requirements worldwide to ensure appropriate reporting of safety information; all clinical studies conducted by the sponsor or its affiliates will be conducted in accordance with those procedures.

### **Method of Detecting AEs and SAEs**

Care will be taken not to introduce bias when detecting AEs or SAEs. Open-ended and nonleading verbal questioning of the parent/caregiver of the subject is the preferred method to inquire about AE occurrence.

#### **12.1. Definitions**

##### **12.1.1. Adverse Event Definitions and Classifications**

###### **Adverse Event**

An AE is any untoward medical occurrence in a clinical study subject administered a medicinal (investigational or non-investigational) product. An AE does not necessarily have a causal relationship with the treatment. An AE can therefore be any unfavorable and unintended sign (including an abnormal finding), symptom, or disease temporally associated with the use of a medicinal (investigational or non-investigational) product, whether or not related to that medicinal (investigational or non-investigational) product. (Definition per International Council for Harmonisation of Technical Requirements for Pharmaceuticals for Human Use [ICH]).

This includes any occurrence that is new in onset or aggravated in severity or frequency from the baseline condition.

Note: The sponsor collects AEs starting with the signing of the ICF to the last study-related activity. In this study, only reportable AEs (respiratory illness AEs and AEs considered at least possibly related to lumicitabine or placebo) and SAEs will be recorded.

Any AEs reported in Study 64041575RSV2004 ongoing at the entry visit of this LTFU study will be considered part of the subject's medical history. If the AE worsens during this study and is a reportable AE or SAE, it will be reported as also occurring in the LTFU study.

